### Approach

**4.a Theoretical Framework:** Self-regulation theory is the theoretical framework for this study. Self-regulation theory involves two tenets: 1) participants manage their response based on their experiences (experiences with pain, depression, and frailty treatments) and knowledge of an event and 2) participants' goals are to maintain comfort and decrease the negative effects of an illness (pain depression and/or frailty) on their lives. The intervention is participant centered and participant driven. This means that the participants' experiences and existing knowledge about pain, depressive symptoms, and frailty will drive the goals that they set. For example, a participant may have experienced pain, depression symptoms, and frailty; she is no longer able to go work in her garden. Her goal may be to be able to garden again. This would provide comfort, decrease the effects of these three conditions, and potentially improve her symptoms.

**Design overview of the study:** The design of the study is outlined in the above figure. The outcomes will determine effect sizes on the intervention's effect on pain and depressive symptoms. Outcomes will be measured at 12 weeks (compare intervention and wait list control group) and at 24 weeks (look at outcomes for wait list control group and outcomes over time for intervention group). Goal attainment will be measured at 12 weeks and 24 weeks. At 24 weeks, we will also conduct virtual semi-structured one on one individual interviews with participants to determine feasibility and acceptability.

The intervention group (n=30) will start the study and will receive eight nurse visits that will be focused on decreasing pain, depressive symptoms, and meeting participant selected goals set in these areas. The wait list control group will receive monthly calls by a study team member to ensure their contact information

has not changed. Data collection, nurse visits, and interviews will be completed via Zoom video calls. Zoom is a HIPAA compliant virtual meeting software used for telehealth purposes. The study will include either in person or virtual visits depending on the preference of the participants. The study team completing in person visits have all been fully vaccinated and will wear personal protective equipment at visits. In addition, study team will screen all research participants for symptoms of COVID based on the Johns Hopkins University of Medicine including fever, cough, sore throat, shortness of breath, acute loss of taste or smell, headache, vomiting or nausea, new fatigue or runny nose in the last 72 hours. The study team will reschedule if participants exhibit any of these symptoms at a later date when participants are symptom free for 72 hours or have a negative Covid-19 test.

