### **2. Objectives**

The aims of this pilot project are to 1) test the Depression and Pain Perseverance through Empowered Recovery (DAPPER) program for feasibility and acceptability. Specifically, we will 1) test the effect size of DAPPER on pain and depressive symptoms from baseline to 12 weeks (compare intervention to wait list control group) and then at 24 weeks to compare the intervention group to wait list control group once again, 2) estimate preliminary effect sizes for DAPPER in reduction of frailty, and 3) measure effect sizes and feasibility of measuring cytokines.

This study is being supported through funding from the Harold Amos Medical Faculty Program and the Johns Hopkins Older Adults Independence Pepper Center.

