## **DAPPER Protocol**

### **Inclusion/Exclusion Criteria**

Inclusion criteria: 1) self-reported pain  $\geq 3$  out of a 0 -10 scale that has lasted longer than 3 months and keeps them from doing at least one activity that they would like, 2) Self-Identify as African American/Black female 3) non-institutionalized and living in the community Maryland, Virginia or Washington DC area. 4) score a 5 or higher on the PHQ9 (depression measure) at least two times during a two week period (screening call and then at first data collection visit via video), 5) pre-frail ( one or two criteria on frailty phenotype) or frail (three or more of the criteria on frailty phenotype), 6) at least one ADL or IADL limitation Exclusion Criteria: 1) Hospitalized  $> 3$  times in the last year, 2) participating in physical therapy, 3) have a terminal diagnosis ( $< 1$  year expected survival), 4)  $\geq$  moderate intellectual impairment (5-7 errors) based on the Short Portable Mental Status Questionnaire (SPMSQ), 5) Unable to understand or speak English

We will recruit participants from the PI's Communication Behaviors and Development of Pain and Depression Intervention among Older African American Women (IRB000170533) study. This study consisted of focus groups for the development of the DAPPER intervention. We will only contact participants who agreed to be contacted for future studies. We will contact these participants by phone and ask them if they are interested in participating in the intervention (please see the phone script). If participants agree to this, we will screen them on the phone at this time.

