**Table 1- Instruments Measuring Main Outcome Variables**

Outcomes	Instruments
Cognition (see inclusion/exclusion criteria)	Short Portable Mini Mental Status Exam 
Depressive Symptoms	Patient Health Questionnaire 9 and Patient Reported Health Outcomes (PROMIS) 57 
Pain	PROMIS Pain Interference, Pain Intensity and Pain Behavior 
Communication	Patients' Reaction Assessment 
Comorbid Conditions	Charlson Comorbidity Index 
ADLS/IADLS	Katz 
Frailty	Frailty phenotype  Frail Scale  will be used to measure frailty.
Stress	Perceived Stress Scale 
Self-Efficacy	Coping and Self-Efficacy Scale 
Readiness to Change	Gitlin and Rose's Readiness to Change Rating System (Gitlin & Rose, )
Social Network Scale	Lubben Social Network Scale
IL6	Saliva Sample
TNF $\alpha$	Saliva Sample
IL8	Saliva Sample
IL-1 $\beta$	Saliva Sample
Goal Attainment	Subjective Report

The following instruments and a demographic questionnaire (e.g. age, SES, and education) will be administered to the participants' pre- and post-intervention.

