##### **Analytic approach:**

For DAPPER, the outcomes will be improvement in pain, depressive symptoms, and communication with health care providers. A database will be created and stored on a password protected encrypted computer. Prior to conducting the analysis, the distribution of the data will be examined to determine if they meet the assumptions of the analytical model and to explore the pattern of missing data. The number of sessions attended will be computed as an indicator of acceptability. To test the effect of the intervention on outcomes (depressive symptoms, pain), generalized estimating equations will be used (GEE) with time, group, and the time x group interaction. We will not be sufficiently powered to detect a significant effect; interpretation of the results will be based on the effect size associated with the time by group interaction for each outcome. One advantage of GEE is it allows all participants' data to be included in the analysis, even those who do not complete the study, providing an intention-to-treat analysis. We will also conduct sensitivity analyses with completers only and compare the effect size to the ITT analysis to estimate the effect size when all participants adhere to the intervention.

Acceptability of the intervention will be examined in multiple ways. We will examine percentages of people who stayed in each arm of the study and conduct numerous descriptive correlational analyses of the

association between the intervention compliance and other variables. These analyses will quantify intervention implementation by demographic and participant health variables. Analyses that utilize the post-randomization data (e.g. treatment compliance) will be evaluated in supplementary analyses. We will distinguish non-compliance with intervention from attrition or loss to follow-up, i.e. missing data. We will also use the one-on-one qualitative interviews to examine acceptability of the intervention.

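### The plan does not settle what the 24-week result estimates, and if the wait list has been treated by then, neither the between-arm contrast nor the within-arm change gives DAPPER's effect size

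*Combined protocol and SAP*

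**What the plan says.** Three parts of the combined protocol and SAP describe the 24-week reading.

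- **Objectives:** after the 12-week comparison, the plan is "then at 24 weeks to compare the intervention group to wait list control group once again".
- **Approach, design overview:** the arms are compared at 12 weeks, but the reading changes to "at 24 weeks (look at outcomes for wait list control group and outcomes over time for intervention group". The sentence that introduces this reads "The outcomes will determine effect sizes on the intervention's effect on pain and depressive symptoms".
- **Analytic approach:** for pain and depressive symptoms, "generalized estimating equations will be used (GEE) with time, group, and the time x group interaction", and "interpretation of the results will be based on the effect size associated with the time by group interaction for each outcome". No time point is attached to that interaction.

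Two parts describe when the wait list starts. The Abstract has it begin once the intervention group has finished its visits. The wait-list paragraph of the DAPPER Protocol has it begin only after the intervention group has completed the study. The Abstract schedules assessments of everyone at the start, 12 weeks and 24 weeks.

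On selection, entry requires participants to "score a 5 or higher on the PHQ9 (depression measure) at least two times during a two week period", the two occasions being "screening call and then at first data collection visit via video". The first data collection visit is also the baseline visit, and the Data Collectors paragraph makes enrolment depend on the frailty, pain and depression criteria checked there. The PHQ-9 is also an outcome measure. The text under Table 1 says the instruments are given "pre- and post-intervention", without saying which visit is the pre-intervention one for the wait list.

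**The concern.** The Sample size paragraph says the effect sizes are for planning a definitive trial, and it expects no significant difference. Point estimates are therefore what will be carried forward. If it is unclear which 24-week quantity counts as the effect, a team could choose between a between-arm contrast that is diluted by crossover and a within-arm change that looks better because it includes the natural fall in scores selected for being high. The first would understate DAPPER. The second could be taken as an effect size, or as proof that the benefit lasts.

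**Working it through.** **1. The readings side by side**

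| Section | 12 weeks | 24 weeks |
|---|---|---|
| Objectives | between arms | between arms again |
| Approach, design overview | between arms | each arm on its own |
| Analytic approach | time-by-group effect size, time point not named | same |

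These are different estimands at 24 weeks. Which of them is usable depends on whether the wait list is still untreated, and on that the Abstract and the DAPPER Protocol differ.

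**2. What each reading estimates**

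Let m be the change from enrolment that would occur without treatment. It is the same in both arms in expectation because they are randomised. Let D be DAPPER's effect, taken as equal in both arms and sustained. For simplicity, take m as the same at 12 and 24 weeks.

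| Reading | Expected value | m = −1, D = 0 | m = −1, D = −2 |
|---|---|---|---|
| Week-12 contrast | (m + D) − m = D | 0 | −2 |
| Week-24 contrast, wait list treated | (m + D) − (m + D) = 0 | 0 | 0 |
| Week-24 contrast, wait list untreated | (m + D) − m = D | 0 | −2 |
| Intervention arm, weeks 0 to 24 | m + D | −1 | −3 |
| Wait list (treated), weeks 0 to 24 | m + D | −1 | −3 |
| Wait list (treated), weeks 12 to 24 | D | 0 | −2 |

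The week-12 contrast recovers D in either case. Once the wait list has crossed over, the week-24 contrast no longer does, and change from week 0 within an arm is off by m.

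**3. How large m could be for the PHQ-9**

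The documents give no PHQ-9 mean, SD or between-visit correlation, so there is no figure of the plan's own to reproduce. Every input below except the entry rule and the 0–27 range of the score is an assumption.

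- Trivariate normal scores (screening, baseline, untreated follow-up), SD 5, rounded and limited to 0–27.
- Entry rule from the plan: at least 5 at both screening and baseline.
- Source mean 4 to 8; screening-to-baseline correlation 0.75 to 0.85; correlation of either score with follow-up 0.5 to 0.7.

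Standardised fall = mean fall ÷ SD of baseline among those enrolled:

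- Smallest (mean 8, correlations 0.75 and 0.7): 0.49 ÷ 3.67 = 0.13.
- Middle (mean 6, correlations 0.8 and 0.6): 1.16 ÷ 3.31 = 0.35.
- Largest (mean 4, correlations 0.85 and 0.5): 2.09 ÷ 2.97 = 0.70.

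About 9% to 32% of enrolled women would score below 5 at follow-up with no treatment.

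The size is sensitive to the model. With source means of 4 to 10 and one constant correlation of 0.5 to 0.85 between all visits, the fall to week 24 is 0.1 to 1.5 points (0.03 to 0.50 SD). If the correlation decays with time, at 0.5 to 0.85 per 12 weeks, it is 0.4 to 3.2 points (0.10 to 1.10 SD). At a source mean of 10 alone, the two models give 0.1 to 0.5 and 0.4 to 1.1 points.

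**4. Starting the wait list from week 12**

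The week-12 score is not a selecting score. From there to week 24 the untreated change is about 0 under constant correlation and 0.2 to 1.0 point downward under decaying correlation. This is smaller, but still uncontrolled.

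**5. Precision of the week-12 contrast**

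With the plan's 25 per arm after attrition, the standard error of a standardised difference is about √(2/25) = 0.283, so the 95% half-width is 1.96 × 0.283 = 0.55. The apparent within-arm change in step 3 is of the same order as this uncertainty.

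**The case against.** The strongest reply is that the Analytic approach governs. It fits group, time and their interaction, and rests interpretation on the interaction. That is a between-arm quantity, so regression to the mean cancels in expectation at both 12 and 24 weeks. The Objectives also plan a between-arm comparison at 24 weeks, and the design overview's choice of verb at 24 weeks can be taken as descriptive. This stands. A reader might infer that the plan will report regression to the mean as a DAPPER effect; the documents do not support that, because no section designates a within-arm change as the effect size.

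A reader might also infer that the wait list's change will be taken from enrolment. That is not established either. The wording under Table 1 fits a week-12 pre-score at least as well, and the Final Data Collection Visit text describes what the collector does, not a change score. Nor is it certain that no untreated comparator exists at week 24: read literally, the DAPPER Protocol could leave the wait list untreated then. The design figure, which is not available, may bear on this.

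On size, the inputs are assumed. Recruitment is partly targeted, through a previous study on pain and depression and providers of chronic pain patients, so a higher source mean and a smaller fall are plausible. No calculation was made for pain. PROMIS depression, pain interference and pain behaviour have no stated entry cut-off, so selection on them is only indirect.

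What the reply does not do is supply a clean 24-week reading. Under the Abstract's timing, the contrast in which regression cancels is also the one in which DAPPER's effect largely cancels. The within-arm readings that the design overview offers under its effect-size sentence are then the natural place to turn.

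**Conclusion.** The point holds as an unsettled 24-week estimand. The Objectives, design overview and Analytic approach do not agree on it, and the Abstract and DAPPER Protocol do not agree on when the wait list starts. If the wait list has been treated by week 24, the between-arm contrast is pulled toward zero, and is exactly zero in expectation if the effects are equal and sustained. Change from the enrolment PHQ-9 then includes a natural fall of about 0.5 to 2.1 points (0.13 to 0.70 SD) for an assumed SD of 5 and source mean of 4 to 8. It is smaller with a higher source mean, and larger if correlation decays with time and the source mean is low. The direction follows from the entry rule; the size is not determined by the documents. Such change may be read as an effect or as durability. The randomised week-12 contrast is not affected. This should be changed, but it does not undermine the pilot.

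**What to change.** - In the Objectives, design overview and Analytic approach, name the week-12 time-by-group contrast as the effect size used to plan the definitive trial.
- Report the 24-week results as descriptive, including the intervention arm's course from week 12 to week 24, and not as an effect size or as proof of durability.
- Take the wait list's change during DAPPER from its own week-12 score, and show it beside that arm's untreated change from week 0 to week 12. The two should not simply be subtracted, because the earlier interval starts from a selecting score and so carries more regression to the mean.
- Reconcile the Abstract and the DAPPER Protocol on when the wait list starts, and state whether that arm is treated or untreated at week 24.

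No new data are needed, since assessments at 0, 12 and 24 weeks are already scheduled. The cost is protocol and analysis wording, and 24-week results that support weaker claims. The planning effect size will also rest on one imprecise contrast, which should be reported with its confidence interval.

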### **1. Abstract**

Older African American women experience disproportionate rates of chronic conditions in comparison to other groups. Pain, depressive symptoms, and frailty often co-occur in African American women aging with chronic conditions and this combination can lead to disability and poor quality of life. Addressing pain and depressive symptoms may improve or delay the progression to frailty. To our knowledge there is little work being done in this population to address both pain and depression. The Depression and Pain Perseverance through Empowered Recovery (DAPPER) program is person directed and will consist of 8 nurse visits during which the nurse assesses each participant for pain, depression, and frailty, then implements a manualized individually tailored intervention. The data collection visits, and nurse visits will take virtually. We propose a pilot trial that is a wait list randomized control pilot to test the acceptability and obtain a preliminary effect size for the intervention. We will recruit 64 ( $\geq$ age 50) African American women who report pain intensity of 3 or higher that interferes with their activities, depressive symptoms lasting more than two weeks, are pre frail or frail, and live in the community/are not institutionalized. The sample will be recruited through the PI's previous study, community recruitment flyers distributed virtually, and word of mouth campaigns. Participants will be randomized into either the intervention or the wait list control group. Once the intervention group has completed their visits, the wait list control group will begin their visits. All participants will be offered the same information and format of nurse visits. The nurses will systematically tailor the content of the visits to the participants' risk profile and goals based on protocols. All participants will be assessed at the start of the study, at 12 weeks, and 24 weeks. The primary outcomes will be pain, depressive symptoms, and frailty status. Other endpoints include goal attainment, stress (cytokines), self-report, self-efficacy, and communication with health care providers. We will also examine the acceptability of the intervention using intervention compliance and one-on-one qualitative interviews. This study will offer either virtual or in person visits based on the preference of the participants.

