- If the signed consent is provided as an electronic copy (dropped off at their place of residence) emailed ,photo/scanned to text, or faxed), the participant or LAR must return the original signed document on their first in person visit or by mail if there is no in person visit.
- If the signed consent form is mailed to the consent designee by the participant or LAR, The IRB-approved consent designee will sign their copy which they possess after the participant has acknowledged signature on their copy. Once the participants original copy is received the consent designee copies will be attached to make a single document.
- If the participant signed consent form is provided immediately by electronic format (emailed, faxed or photo/scanned to text, once received, the IRB-approved consent designee signs, dates/times this informed consent document.

We will provide participants with password protected ZOOM links for all meetings.

We will distribute flyers to the Maryland AARP, senior housing residents, African American hair salons, and on Facebook local group and organization sites. A study team member will obtain necessary permission from administrative staff at all locations before any flyers are distributed via postal mail or email.

We will randomize participants to each group with the following process. 1) Once we find potentially interested participants through the above referral sources, we will telephone screen for eligibility and explain study procedures. 2) If eligible by phone, the research assistant will re-screen, re-explain the study, obtain consent (via DocuSign or hard copy ), and conduct the baseline data collection. 4) If participants qualify for the study after this visit, within 48 hours of the baseline interview, we will randomize using a computer-based assignment scheme and communicate the assignment to participants by letter. An employee of the Johns Hopkins Center of Innovative Care in Aging will be unblinded and will complete the randomization for the project. 5) The person assigned to randomize will inform the nurses of the participants' group (intervention or control). 7) The nurses will contact the participant within one week to schedule the first appointment.

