The wait list control group will have data collectors schedule a Zoom video visit with them. The same data will be collected for the intervention group. Participants in the wait list control group will not start the DAPPER intervention until the intervention group has completed the study. The wait list control group will receive monthly phone calls to confirm contact information.

**Data Collectors:** The data collectors have been trained to obtain baseline and outcome measures of each participant. The data collectors will collect baseline and outcome data and are responsible for teaching the participants how to collect saliva samples. The data collectors will call participants to schedule the first Zoom video call. The data collector will call/log on at the mutually agreed time. The data collector will complete the questionnaire booklet with the participant and complete the frailty phenotype measurements

with the participant. If the participants meets the criteria for frailty, pain, and depression, enrollment in the study will continue. Upon completion of the nurses' visits, the data collectors will schedule a final visit with participants.

**Research Nurses:** An RN is the appropriate professional to conduct the visits because of the training in assessment skills, and knowledge base in physiology, medications, and patient education in pain and depressive symptoms. The nurses have been trained on the protocol. The nurses will call the participants to schedule the first visit. The nurses will meet with participants via Zoom video calls during a mutually agreed upon time. The nurses will work with participants to set goals surrounding pain and depressive symptoms. The goals will be participant driven and documented by the nurse. The nurse will then work with the participant to identify strategies to work on three goals.

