After the informed consent process is completed, the IRB approved study team member files the consent document in the research record, including a note confirming the consent process. The data collector will verify if the participant has any questions regarding the consent form and verify the participant understands the consent form. The data collector will ensure that the participant reads the consent form and has a copy of the consent form. After the consent is completed, a formal assessment of outcomes will be done. The data collector will explain the process of saliva sample collection to the participant. We will not collect saliva samples from participants outside of Maryland. A kit will be dropped off to the participants with non-contact either at their door or given to front office. We will call and confirm participants receive the kits. The participants will be asked to store samples in their home refrigerator. If there is not a working refrigerator, the participants will be provided with a cooler and ice packs that will be replaced over the two days. When the participant is ready for the saliva sample to be picked up, they will notify us, and it will be picked up using protective gear (gown, gloves, and mask) without contact with participants and stored in the Johns Hopkins School of Nursing lab.

**Final Data Collection Visit:** At this visit, the data collector will enact the same protocol as at baseline.

**Saliva Sample Visits:** A member of the research staff will contact the participants to ask them a good time to pick up samples. The research staff member will arrive to participants home to pick up samples. Personnel picking up the samples will notify participants when they are arriving, and participants will place the sample outside the front door once the staff member pulls up or walks up to their home location. The staff member will label the specimens and take them directly to the Johns Hopkins School of Nursing refrigerator. Please see specifics below (laboratory studies) for further information about the collection and storage process of the saliva samples.

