**Comorbid Conditions:** We will measure comorbid conditions with the Charlson Comorbidity Index. The Charlson comorbidity index consists of 17 categories of chronic conditions including two subcategories for diabetes and liver disease. Comorbidities are based on mortality risk and severity of the disease; the scores for each disease range from 1-6. A final Charlson Comorbidity Index score is compiled; scores greater than or equal to five indicate more chronic conditions and increased risk of mortality.

**Physical Function:** Physical function will be assessed by measuring ADLs Katz ADL and Lawton's IADL measures. On Katz's ADLs scores range from 0-6 with 6 indicating full function and a score of 2 or less indicating sever functional impairment. On Lawton's IADL instrument scores range from 0-8 and higher scores indicate better physical function.

**Frailty** will be assessed by the physical frailty phenotype (includes gait speed, grip strength, BMI, and measures of physical activity and exhaustion). The frailty phenotype is used to determine if a person is robust (score of 0), pre-frail (score of 1 or 2), or frail (score of 3-5). The Frail Scale will be used to measure frailty for virtual data collection visits. The Frail Scale asks self-report questions about fatigue, resistance, ambulation, illnesses, and loss of weight.

**Stress** will be measured by perceived stress as it often accompanies depression and/or pain. We will measure using the perceived stress scale. The scores can range from 0-40; higher scores indicate more perceived stress.

**Self-efficacy** is a large part of self-regulation. We are going to measure self-efficacy using the coping and self-efficacy scale. The scores range from 0-26 with higher scores indicating more self-efficacy.

**Readiness to change** will be used to identify participants' readiness to change. The levels include 1-pre-contemplation, 2-contemplation, 3- preparation, and 4- action and maintenance. This will allow the nurses to identify where participants are on this scale and determine if strategies or goals need to be adjusted or reevaluated based on readiness to change scores.

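### Visit mode follows participant preference and nothing holds a woman's assessment mode, or her frailty instrument, constant once she knows her arm

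*Combined protocol and SAP*

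**What the plan says.** **Mode.** The Abstract says "This study will offer either virtual or in person visits based on the preference of the participants", and the Approach section (design overview) repeats it: "The study will include either in person or virtual visits depending on the preference of the participants". A little earlier, the same Approach paragraph says "Data collection, nurse visits, and interviews will be completed via Zoom video calls". The first two sentences allow a choice and the third does not.

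**Allocation.** The randomisation steps, set out under Inclusion/Exclusion Criteria, place allocation after the baseline visit: "within 48 hours of the baseline interview, we will randomize using a computer-based assignment scheme and communicate the assignment to participants by letter". No stratification factor is named.

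**Follow-up.** The nearest thing to a constancy rule is the description of the final data collection visit under Visits: "At this visit, the data collector will enact the same protocol as at baseline". It does not mention mode.

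**Measurement.** The Data Collectors paragraph has the collector complete the questionnaire booklet with the participant. The frailty entry under Outcomes describes the physical phenotype, which includes gait speed and grip strength, and then adds "The Frail Scale will be used to measure frailty for virtual data collection visits".

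**Analysis.** The Analytic approach fits GEE with time, group and their interaction for pain and depressive symptoms, and interprets the effect size of the interaction. The model has no term for mode, and no sensitivity analysis by mode is planned.

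**The concern.** A woman has her baseline assessment before anyone knows her arm, but she chooses the mode of each later assessment knowing it. The two arms also have different contact with the study before week 12: eight nurse visits in one, monthly calls to confirm contact details in the other. Preference for a home or video assessment could therefore move differently in the two arms.

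If it does, part of the apparent change from baseline is a change in how the outcome was measured. The exposure is plainest for frailty, which the Abstract lists as a primary outcome. The Frail Scale asks about fatigue, resistance, ambulation, illnesses and weight loss, whereas the phenotype uses performance tests, BMI, activity and exhaustion. Pain, mood and stress scores are exposed to the extent that answers depend on whether the data collector is in the room or on a screen.

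The pilot exists to supply effect sizes for a definitive trial. A measurement artefact in those effect sizes would be carried into its planning.

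**Working it through.** **1. What the documents supply.** They give the preference rule, the timing of allocation, the instrument rule and the analysis model, all cited above. They do not give the share of women choosing each mode, the share who switch, the effect of mode on any score, or the agreement between the two frailty instruments. There is no figure in the plan to reproduce on this point.

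**2. Is mode held anywhere?** The final-visit sentence fixes the protocol but not the mode, and the description of the first data visit itself allows either a call or video. It also covers only a visit called final, while the Abstract schedules assessments at both 12 and 24 weeks. The Data Collectors paragraph has the phenotype completed in what it describes as a Zoom call, whereas the frailty entry assigns virtual visits the Frail Scale. So even the baseline instrument is not settled by the text.

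**3. How a switch enters the estimate.** Suppose in-person assessment shifts a score by *m* SD. For each arm let *s* be the share assessed in person at follow-up minus the share at baseline. Then:

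- estimated time-by-group effect = true effect + *m* × (*s* in the intervention arm − *s* in the wait-list arm).

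Three cases follow:

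- Mode held constant for every woman: both *s* are 0, so the bias is 0.
- Equal net switching in both arms: the difference is 0, so the bias is 0.
- Unequal net switching: the bias is *m* times the difference.

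The quantity that matters is the between-arm difference in *change* of mode, not in the in-person share itself.

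**4. Illustrative size (all inputs assumed).**

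| Difference in switching | Mode effect | Bias |
|---|---|---|
| 10 points | 0.1 SD | 0.10 × 0.1 = 0.01 SD |
| 30 points | 0.3 SD | 0.30 × 0.3 = 0.09 SD |
| 50 points | 0.5 SD | 0.50 × 0.5 = 0.25 SD |

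For frailty, suppose the two instruments differ by 5 to 20 percentage points in the share classed as frail. The bias then runs from 0.10 × 5 = 0.5 to 0.50 × 20 = 10 percentage points.

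**5. Against sampling error.** The plan states 25 retained per arm, and 32 × 0.87 = 27.8, about 28, follows from its 13% attrition. The standard error of a standardised difference at one time point is about √(2/n):

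- n = 25: √(2/25) = 0.28, 95% half-width 1.96 × 0.283 = 0.55
- n = 28: √(2/28) = 0.27, 95% half-width 1.96 × 0.267 = 0.52

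The middle illustration, 0.09 SD, is about a third of one standard error. The largest, 0.25 SD, is just under one.

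**The case against.** The strongest reply is that the operational text mostly describes Zoom, that the final visit repeats the baseline protocol, and that nothing shows any woman would switch. In an openly underpowered pilot, a bias within the illustrated range is smaller than one standard error. Offering a choice to frail older women is also a legitimate design decision. All of this stands as a limit on importance. It does not close the gap, because the preference rule is stated twice and the final-visit sentence does not mention mode. Unlike sampling error, the bias would not shrink in a larger trial that kept the same rule.

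A reader might infer three stronger points, none of which the documents support.

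- **A planned difference in mode between arms.** The sentence "The wait list control group will have data collectors schedule a Zoom video visit with them" could suggest that only controls are assessed by video. The same section also describes the data collectors' first call and the nurses' visits as Zoom, and says the same data are collected in the intervention arm. No asymmetry is planned.
- **Delivery mode confounding the 12-week contrast.** Up to then the wait-list arm has only contact calls, so it has no delivery mode to compare. The format of nurse visits is part of the intervention.
- **A need to stratify randomisation by mode.** Chance imbalance in mode is not bias. If each woman's mode is constant, an additive mode effect is present at baseline and follow-up alike and drops out of the interaction.

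Nor do the stated aims include a comparison of the two formats, so the absence of one is not a failure of the pilot.

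**Conclusion.** The point holds as a gap in the assessment rule. Mode is left to preference, the text contradicts itself on whether a choice exists, and nothing keeps assessment mode or frailty instrument constant after a woman learns her arm. A change of mode that differs by arm would enter the time-by-group effect for pain and depressive symptoms, and the frailty effect size sought in the Objectives, with nothing in the planned model to absorb it.

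The bias is possible, not shown, and its size cannot be derived from the documents. The range in the working rests wholly on assumed switching and mode effects, and is zero if switching is absent or balanced. The design figure was not available to check. This is a cheap improvement to the plan, not a defect that undermines the pilot.

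**What to change.** 1. Reconcile the Zoom-only and preference statements in the Abstract, Approach and DAPPER Protocol sections, and state which frailty instrument applies in each mode.
2. If choice is kept, record each woman's assessment mode at the baseline data visit, before randomisation.
3. Hold her 12- and 24-week assessments, and her frailty instrument, in that mode in both arms. Allow a switch only where she would otherwise be lost, and record it.
4. Record the mode of every assessment and nurse visit. Nurse-visit mode can stay with preference.
5. Report assessment mode and switches by arm at each time point. Add a sensitivity analysis that excludes switched assessments or adjusts for mode. Exclusion after randomisation is itself selective, so this supports the main analysis and does not replace it.

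The cost is a field on the visit form, a few sentences in the protocol and one extra analysis. The downside is slightly less flexibility at follow-up, which the recorded exception limits. The randomisation scheme need not change.
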